1(0.7	Sample Transfer to sites outside the Organisation	.18
11	Asse	ssment of Safety	.19
	11.1	1 Reporting Responsibilities	.20
1	1.2	Ethics Reporting	.20
1	1.3	Ethics & Regulatory Approvals	.20
12	Com	pliance and withdrawal	.20
12	2.1	Subject compliance	.20
1:	2.2	Withdrawal / dropout of subjects	
1:	2.3	Protocol Compliance	
13	Data	·	
1:	3.1	Data to be collected	.21
1:	3.2	Data handling and record keeping	.21
14	Stati	stical considerations	.22
14	4.1	Sample size calculation (some pilot/feasibility studies may not require a formal	
Sa	ample	size calculation)	.22
14	4.2	Statistical analysis	.22
14	4.3	Interim analysis and data monitoring	.25
	14.3	1 Stopping / discontinuation rules and breaking of randomisation code	.25
	14.3	2 Monitoring, quality control and assurance	.25
15	Ethic	al considerations	.23
16	Fina	ncing and Insurance	.23
17	Repo	orting and dissemination	.23

Guy's and St Thomas' NHS

NHS Foundation Trust

List of Abbreviations and Definitions

AE	Adverse Event
AR	Adverse Reaction
ASR	Annual Safety Report
CA	Competent Authority
CI	Chief Investigator
CRF	Case Report Form
CRO	Contract Research Organisation
DMC	Data Monitoring Committee
EC	European Commission
GAfREC	Governance Arrangements for NHS Research Ethics Committees
ICF	Informed Consent Form
ISRCTN	International Standard Randomised Controlled Trial Number
MA	Marketing Authorisation
MS	Member State
Main REC	Main Research Ethics Committee
NHS R&D	National Health Service Research & Development
PI	Principal Investigator
QA	Quality Assurance
QC	Quality Control
Participant	An individual who takes part in a clinical trial
RCT	Randomised Controlled Trial
REC	Research Ethics Committee
SAE	Serious Adverse Event
SDV	Source Document Verification
SOP	Standard Operating Procedure
SSA	Site Specific Assessment
TMG	Trial Management Group
TSC	Trial Steering Committee

4 Summary/Synopsis

Title	Biomarkers of relapse in ulcerative colitis patients after
	tofacitinib dose reduction
Protocol Short Title/Acronym	BRITE
Protocol Version number and Date	Version 1.0, 07/06/2021
IRAS Number	276727
REC Reference	
Sponsor Reference	
Study Duration	44 weeks
Methodology	Prospective observational study
Sponsor name	GSTT
Co-sponsor name	King's College London
Chief Investigator	[name]
Funder Name	Pfizer
Medical condition or disease under	Ulcerative Colitis
investigation	
Purpose of clinical trial	To identify markers predictive of disease flare in
	ulcerative colitis patients who responded to the higher
	dose commencing on maintenance tofacitinib therapy.
Primary objective	To identify biochemical and genetic markers predictive of
	ulcerative colitis flare
Secondary objective (s)	To identify clinical and disease characteristics predictive
	of ulcerative colitis flare
Number of Subjects/Patients	50 patients
Trial Design	Prospective observational study
Endpoints	1. Flare requiring drug discontinuation, surgery
	(colectomy) or addition of new therapy for ulcerative
	colitis.
	2. Endoscopic activity at week 44 endoscopy
Main Inclusion Criteria	Ulcerative colitis patients commencing tofacitinib
	maintenance dosing, undergoing endoscopy as part of
	their routine clinical care.
Statistical Methodology and Analysis	Receiver operator curves will be generated to determine
	optimal cut-offs for continues variables, predictive of
	disease flare.
	Kaplan-Meier curves will be generated to allow
	comparisons of subdivisions of patients based on genetic
	and biochemical variables, using determined cut-offs.
	Univariate and Multivariate analyses will be performed on
	clinical, biochemical and genetic variables to establish
	predictors of disease flare.

5 Introduction

Tofacitinib has been shown in large-scale randomised clinical trials to be an effective treatment for patients with moderate to severe UC that is resistant to both conventional treatment and to biologic therapy¹. In the few months it has been available in the UK, our unit has accrued some of the biggest experience in the country. Our initial experience and prospectively collected observational data suggest that the drug performs at least as well as clinical trial results would indicate.

Results from the OCTAVE clinical trial program led to the approval of an induction regimen of 10mg BD, with subsequent dose reduction in responders to 5mg BD after at least 8 weeks. This maintenance regimen was shown to maintain remission with greater efficacy than placebo¹. However, the clinical trial data further suggests that in patients who have previously failed anti-TNF therapy, the 10mg BD maintenance dose is superior to the 5mg BD dosing¹. Anecdotally, many clinicians are accordingly favouring continuing the 10mg bd dose in higher risk patients (biologic failures) for up to 52 weeks, rather than dropping to the maintenance dose at week 8.

Inevitably, our early experience is in a largely anti-TNF and vedolizumab experienced cohort; nonetheless, response rates appear to be favourable. The decision to dose reduce these patients must be carefully considered, particularly in view of their previous biologic failures and hence limited options should they fail tofacitinib. Recent extension studies from the original clinical trials have shown that only 64.9% and 49.1% of patients who flare after dose de-escalation are able to recapture response and remission, respectively, on dose re-escalation².

The risk of flare with dose reduction needs to be balanced against the potential risk of continuing at the 10mg bd dose. There is a clear dose response in terms of the risk of herpes zoster^{1,3,4}, and recent communication from a trial of patients with rheumatoid arthritis has suggested that there may be other safety signals in the form of greater risk of venous thromboembolism with the higher dose².

Therefore, given that many patients who are receiving tofacitinib will be biologicexperienced, there is an urgent need to identify biomarkers that might predict those more likely to flare should they dose reduce. Such biomarkers would enable us to risk stratify our patients at the point of consideration of dose reduction, to enable assessment of the risk and benefit of dose reduction versus continuation at the higher dose. By extension, predictors would enable us to maintain higher dosing in those more likely to flare with dose reduction, justifying the additional risk. To the best of our knowledge, there is neither any data already in existence that addresses this field, nor are there any ongoing trials. As IBD enters the era of personalised/precision medicine, gaining a deeper understanding of the best use of our most efficacious agents, such as tofacitinib, appears an essential endeavour.

This study aims to explore 3 novel areas for predictive biomarkers, in addition to assessing the predictive capability of baseline (defined here as the point of dose reduction) clinical, endoscopic and histologic markers. We hypothesize that patients who relapse following dose reduction to maintenance dose tofacitinib will have changes in cytokine expression of their pro-inflammatory effector T cells in peripheral blood mononuclear cells (PBMCs), increased

STAT activation in PBMCs, and possibly signature genes in their colonic tissue that may predict relapse. Accordingly, we aim to address 3 novel questions:

1. Is there increased activation of STAT proteins in peripheral blood in patients who relapse?

The direct molecular targets of cytokine-induced JAK tyrosine kinases are the signal transducers and activators of transcription (STAT) proteins, which when phosphorylated become activated and translocate to the nucleus to bind DNA and induce cytokine specific gene expression and chromatin regulation⁵. STAT proteins are key molecular regulators of CD4-T-helper (Th) cell lineage differentiation programmes, which are directed and propagated following specific signature cytokine cues⁶. Aberrant activation of STATs is, thus, often a critical step in the molecular pathogenesis of several inflammatory and auto-immune diseases, that are associated with dysregulated Th function^{7,8}. Of the 7 STAT proteins, increased activation of STAT1, STAT3, and STAT5a/b in particular, and to a lesser extent STAT4 and STAT6, have been associated with the pathophysiology of UC, consistent with their activation by inflammatory cytokines involved in UC pathogenesis, such as IFNγ, IL12 (TH1), IL4, IL6, IL13, IL21 (TH2), IL6, IL23 (TH17), IL9 (TH9)⁹⁻¹³. Therefore, we will monitor the phosphorylation of STAT proteins in PBMC from patients enrolled in the study, with blood drawn before dose reduction.

2: Are there changes in cytokine expression in peripheral T cells that predict relapse?

The immunopathogenesis of IBD, including UC, is driven by the dysregulated expression of specific proinflammatory cytokines, secreted primarily by CD4 T-effector cells, which critically drives inflammation and tissue destruction¹⁴. These cytokines mediate their actions via STAT proteins, which are the subject of evaluation in question 1 above. To understand if there are changes in cytokine expression that predict relapse in specific patients, we will evaluate cytokine expression in peripheral CD4 T cells. The cytokines we will study are the key CD4 T-effector cytokines IFN γ , IL17, and IL9 corresponding to TH1, Th17 and Th9 lineages, that have been implicated in the pathogenesis of UC. These data will inform us of any changes in peripheral levels of pathogenic cytokines that predict patients who will relapse following tofacitinib dose reduction.

3: Can we identify signature gene(s) that serve as a biomarker to predict relapse?

Changes in immune homeostasis that predict relapse following dose reduction are most likely to be identified at the site of inflammation. The distinctive molecular changes that underlie the loss of immune homeostasis prior to relapse can be identified by studying gene expression changes in colonic tissue, as has previously been done to predict response to infliximab treatment¹⁵. We wish to compare gene expression changes between patients who remain symptomless on the lower dose of tofacitinib with those patients who ultimately show clear clinical signs of relapse. We expect that the differential gene expression (DEG) list may contain negative regulators of cytokine signaling (SOCS proteins) and/or inhibitors of STAT proteins (PIAS proteins), whose activity critically regulates the functional activation of STAT proteins and downstream cytokine induced gene expression. These studies will identify genes that can be used as biomarkers for relapse following tofacitinib dose decrease and also help in identifying genes that can be more rapidly screened in blood for the purpose of predicting relapse in patients in the clinic.

NHS Foundation Trust

4: Using immune monitoring of the mucosal immune system to identify biomarkers of relapse and remission.

We have the opportunity to systematically collect tissue from patients with UC treated with tofacitinib, as such we will undertake to track the mucosal immune response by multiparametric flow-cytometry study on endoscopic biopsies of the 50 patients within the BRITE study. These biopsies will be excess to these required to undertake the agreed experiments as part of the original study proposal – hence this proposal is of added benefit and will not detract from the funded study. This will facilitate flow cytometric immune monitoring of the architecture of the mucosal immune system (T cells, B cells and the myeloid compartment) at the point of de-escalation. Patients will subsequently be followed to relapse or the end of the study, whichever comes first, and tissue resampled to investigate the longitudinal changes in immunophenotype in the context of response to therapy. Similar immune monitoring has proved crucial at defining immune signatures in SARS-CoV-2 infection (15). This study is complementary to the work being performed in the original BRITE proposal and will provide more information on the effect of the drug on immunophenotypes and identify immunological signatures of response and or relapse – allowing a precision approach to drug selection.

6 Trial objectives and purpose

This is an investigator-initiated study with an overarching objective to identify biochemical and genetic markers of patients more likely to flare after tofacitinib dose reduction. It is hoped that this will eventually allow us to target continued higher dosing of 10mg bd at those patients who are most likely to benefit from it and avoid its use in patients in whom it is potentially unnecessary. Thereby, it would enable using the drug in a safer, more effective and more economical manner.

Primary objective:

• To identify biochemical, histologic and genetic markers predictive of ulcerative colitis flare in patients on tofacitinib commencing on maintenance 5mg BD dosing.

Secondary objectives:

- To identify clinical characteristics predictive of ulcerative colitis flare in patients on tofacitinib commencing on maintenance 5mg BD dosing.
- To identify predictors of endoscopic activity at week 44

7 Study design & Flowchart

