7.1 Study Design

This is a prospective observational study. We will prospectively enroll a cohort of 50 UC patients who have achieved an adequate response to tofacitinib at a dose of 10mg bd and whose dose is being reduced to 5mg bd following a routine flexible sigmoidoscopy. Colonic

tissue and blood samples will be collected at study entry, and patients' disease course will be followed-up through routine care.

Week 44 has been chosen for the primary endpoint, as 44 weeks post dose de-escalation was used as the endpoint in OCTAVE Sustain.

Primary endpoint:

• Biomarkers, clinical markers and histological markers associated with ongoing treatment with 5mg bd in the absence of steroids at week 44.

Secondary Endpoints

• Biomarkers, clinical markers and histological markers associated with steroid free endoscopic remission at routine endoscopy at week 44

Biomarkers / outcome measures will include:

- Clinical status (SCCAI)
- CRP and faecal calprotectin (as part of routine care)
- Histological markers of disease activity (Nancy histological index) (as part of routine care)
- STAT activation in peripheral blood mononuclear cells
- Cytokine expression in peripheral T cells
- Gene signatures in colonic biopsies

Guy's and St Thomas' MHS

NHS Foundation Trust

Flow Diagram

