9.3 Schedule of Assessment for each visit

Patients in whom the treating team is planning to reduce their Tofacitinib from 10mg BD to 5mg will be referred for consideration of inclusion in the study.

- 1. Screening phone call
 - a. Information regarding the study provided
 - b. Inclusion/exclusion criteria reviewed
 - c. Patient information sheet, and consent form sent to patient in the mail or via e-mail.
- 2. Routine baseline endoscopy
 - a. Informed consent gained and form signed, prior to the endoscopy.
 - b. Baseline clinical data collected
 - c. Endoscopy performed and biopsies taken from rectum and sigmoid, to be sent for:

Guy's and St Thomas' Miss

NHS Foundation Trust

- i. Histological assessment of disease activity (Nancy Histological Index)
- ii. Genetic analysis
- iii. Future exploratory analysis
- d. Blood collection, to be sent for:
 - i. Routine clinical bloods (FBC, CRP, LFTs, U&E)
 - ii. STAT activation in peripheral blood mononuclear cells
 - iii. Cytokine expression in peripheral T cells
- e. Faecal calprotectin submitted
- 3. Flare (SCCAI \geq 5)
 - a. Should a clinical flare occur, patients will be encouraged to contact our IBD advice line as per current standard of care.
 - b. Routine and study blood tests, stool, and endoscopic tests will be initiated, as per standard of care, and the decision on how to manage the clinical flare will be taken by the treating team. Additional study biopsies will be taken at the time of the endoscopy.
- 4. Routine clinical visits
 - a. These will occur as per the treating team's discretion, with testing performed accordingly.
- 5. Week 44
 - a. In patients who remain on tofacitinib at week 44, routine clinical assessment will occur.
 - b. Tests performed will be
 - i. Routine endoscopy and biopsies, sent for:
 - 1. Histological assessment of disease activity (Nancy index) (part of routine care)
 - ii. Study biopsies, sent for:
 - 1. Genetic analysis
 - 2. Future exploratory analysis
 - iii. Routine blood collection, to be sent for:
 - 1. Routine clinical bloods (FBC, CRP, LFTs, U&E)
 - 2. Study blood tests will also be taken at this time point
 - iv. Routine faecal calprotectin

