13.1 Data to be collected

Data will be collected by the study investigators.

Data at the various time points include:

- Baseline:
 - Demographic data, disease extent history, concomitant medications, previous IBD medications, smoking history from patient history and notes.
 - Simple Clinical Colitis Activity Index (SCCAI), calculated by the assessor •
 - Serum CRP and albumin, and faecal calprotectin
 - Endoscopic Mayo Score, recorded by the endoscopist
 - Nancy histological index, reported by the pathologist •
 - STAT activation in peripheral blood mononuclear cells, recorded from • laboratory data
 - Cytokine expression in peripheral T cells, recorded from laboratory data
 - Gene and T/B cell receptor analysis in colonic biopsies, recorded from laboratory data
- Flare
 - Time point, alteration to treatment, faecal calprotectin, CRP, SCCAI, endoscopic Mavo score (if endoscopy performed), all recorded by the investigator from the patient notes.
 - Gene signatures in colonic biopsies, recorded from laboratory data
- Week 44
 - CRP, albumin, SCCAI, calprotectin, recorded from the patient's notes. •
 - Endoscopic Mayo score, recorded by the endoscopist
 - Nancy histological index, reported by the pathologist
 - STAT activation in peripheral blood mononuclear cells, recorded from laboratory data
 - Cytokine expression in peripheral T cells, recorded from laboratory data
 - Gene signatures in colonic biopsies, recorded from laboratory data

In the event of incomplete data, patients will be telephoned to arrange completion.

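### Synopsis endpoint 1 scores a flare rescued by return to 10mg bd as no event, in conflict with section 7.1, section 9.3 and the study aim, and section 14.2 does not say which outcome is analysed

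*Protocol*

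**What the plan says.** The protocol describes the outcome in several places.

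- **Section 4, Endpoints.** Endpoint 1 is "Flare requiring drug discontinuation, surgery" (colectomy) "or addition of new therapy for ulcerative" colitis. The three consequences form a closed list, and a dose increase is not among them.
- **Section 7.1.** The primary endpoint concerns markers "associated with ongoing treatment with 5mg bd in the absence of steroids at week 44".
- **Section 9.3.** The flare visit is defined by an SCCAI of 5 or more, whatever treatment follows. Management of the flare is left to the treating team.
- **Section 5.** Re-escalation is foreseen. The protocol reports that only 64.9% and 49.1% of "patients who flare after dose de-escalation are able to recapture response and remission, respectively, on dose re-escalation".
- **Section 6.** The overarching objective is to "identify biochemical and genetic markers of patients more likely to flare after tofacitinib dose reduction", so that continued 10mg bd can be directed at those most likely to benefit.
- **Section 13.1.** The data recorded at flare include "Time point, alteration to treatment, faecal calprotectin, CRP, SCCAI".
- **Section 14.2.** The ROC, Kaplan-Meier and regression analyses concern predictors of disease flare. The section does not refer to any of the definitions above. The synopsis carries the same analysis text.

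**The concern.** On its plain wording, endpoint 1 does not cover a return from 5mg to 10mg bd: the drug continues, there is no surgery, and no therapy is added. It therefore records flares that re-escalation did not rescue, not flares after dose reduction. A patient who relapsed on 5mg bd and recovered on 10mg bd gets the same code as one who never relapsed.

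If this event feeds the analyses, two things follow. Patients who failed dose reduction sit in the comparison group, so a real marker difference is diluted. The question also shifts from who flares on 5mg bd to who cannot be recaptured, which is not the objective in section 6. Two analysts following different sections could code the same patient in opposite ways.

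**Working it through.** **Step 1: one patient under each definition.** Take a patient who flares at week 12 with an SCCAI of 5 or more, returns to 10mg bd, recovers without steroids or any other added agent, and is on 10mg bd at week 44.

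| Source | Rule | Score |
|---|---|---|
| Section 4, endpoint 1 | Discontinuation, colectomy or new therapy | No event |
| Section 7.1 primary endpoint | On 5mg bd without steroids at week 44 | Failure |
| Section 9.3 | SCCAI of 5 or more | Flare |
| Section 14.2 | Disease flare, not defined | Undetermined |

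The synopsis is the outlier. If the patient later stops the drug, has a colectomy or starts another therapy, endpoint 1 does count an event, but later than the flare.

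**Step 2: how many flares could be missed.** The plan has no figure to reproduce. Section 14.1 gives no sample size calculation, and no flare rate or re-escalation share is stated. From the protocol: N = 50, and recapture r = 0.649 (response) or 0.491 (remission). Assumed: flare rate f and share of flares re-escalated q. Also assumed: a re-escalated flare that is not recaptured later meets a listed criterion, and a recaptured patient receives nothing that counts as new therapy.

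Missed = N × f × q × r. Share of the non-event group that in fact flared: c = missed / (N − N × f + missed).

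With f = 0.4 (20 flares):

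| q | r | Missed | Flares counted | Non-event group | c |
|---|---|---|---|---|---|
| 0.5 | 0.491 | 20 × 0.5 × 0.491 = 4.9 | 15.1 | 34.9 | 0.14 |
| 0.5 | 0.649 | 20 × 0.5 × 0.649 = 6.5 | 13.5 | 36.5 | 0.18 |
| 1.0 | 0.491 | 20 × 0.491 = 9.8 | 10.2 | 39.8 | 0.25 |
| 1.0 | 0.649 | 20 × 0.649 = 13.0 | 7.0 | 43.0 | 0.30 |

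Over f = 0.2 to 0.6, q = 0.25 to 1 and both recapture rates, between about 1 and 20 of the 50 patients are miscoded, and c runs from 0.03 to 0.49.

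**Step 3: what this does to a marker.** Assume a true AUC of 0.75, with missed and counted flares sharing one marker distribution. Against a missed flare, a counted flare has an AUC of 0.5, so the observed AUC is (1 − c) × 0.75 + c × 0.5 = 0.75 − 0.25c.

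- Half re-escalated: 0.75 − 0.25 × 0.14 = 0.71, and 0.75 − 0.25 × 0.18 = 0.71.
- All re-escalated: 0.75 − 0.25 × 0.25 = 0.69, and 0.75 − 0.25 × 0.30 = 0.67 (c unrounded is 0.302).

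Simulating a two-sided 5% rank test under the same assumptions gives power of about 0.87 to 0.88 with nothing missed, 0.6 to 0.7 with half re-escalated, and 0.3 to 0.45 with all re-escalated.

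**The case against.** The strongest reply is that the omission is not protocol-wide. The only endpoint labelled primary is in section 7.1, and it already treats a patient on 10mg bd at week 44 as a failure. Section 9.3 already calls that patient a flare. Section 14.2 speaks of disease flare, and nothing ties that phrase to synopsis endpoint 1. If either of the other definitions is the analysed outcome, the misclassification does not arise. A reader might infer that the study as a whole scores rescued flares as non-events. The documents do not support that. They support a conflict between definitions, one of which does so.

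The size is also open to challenge. The flare rate, re-escalated share and AUC are not in the protocol. The recapture rates come from extension studies of the original trials, while section 5 describes the local patients as largely biologic-experienced. A recaptured patient who also received steroids or another agent may already count under the new-therapy limb, so the missed share is an upper limit. The endpoints are called exploratory, so no planned power is lost.

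Finally, a stricter treatment-failure composite can be defended, because section 5 stresses how few options remain after tofacitinib fails.

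All of this limits the claim but does not remove it. Endpoint 1 is the synopsis's only listed endpoint that mentions flare, and it stands beside the same analysis text as section 14.2, so it is a natural candidate for the analysed event. Reading a dose increase as a new therapy would stretch the words, and that uncertainty would itself need settling. A stricter composite is legitimate only if it is chosen openly, because it answers a different question from section 6.

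**Conclusion.** The point holds as an inconsistency with a definite consequence. On its plain wording, synopsis endpoint 1 scores a flare rescued by return to 10mg bd as no event. That contradicts section 7.1, section 9.3 and the aim in sections 5 and 6, and section 14.2 leaves the choice of outcome open.

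If the synopsis event is the one analysed, the missed share of flares is at most the re-escalated share times 49.1% to 64.9%. The direction, toward the null, rests on missed flares resembling counted flares on the marker. The patient counts, AUCs and power values are illustrations under stated assumptions. They should not be read as estimates for this cohort or as a shortfall against a planned power. Severity: should fix.

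**What to change.** Reconcile sections 4, 7.1, 9.3 and 14.2 into one event definition before any marker result is seen. Recoding after that point would invite choosing the outcome by its result.

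- In the synopsis list, add re-escalation of tofacitinib dose for flare as a qualifying event, and date the event at the first qualifying component.
- In section 14.2, name this event as the outcome of the ROC, Kaplan-Meier and regression analyses of flare, and state how it relates to the week 44 endpoint in section 7.1 and to the SCCAI threshold in section 9.3.
- Tabulate the original components (discontinuation, colectomy, new therapy) separately, so that the stricter outcome stays visible.

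The cost is a few lines of text. Section 13.1 already records the time point and the treatment change at flare, so no new data are needed. The small downside is that the composite then includes a less severe event. The change affects only how outcomes are scored, not how any flare is treated.
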